2.5 Sample size and power considerations

The alpha (α) level of 5% is split to CV death at 4% and to WHF at 1%. The sample size calculation is based on the CV death endpoint. This is an event-driven trial with fixed maximum duration of 180 day follow-up period for each patient. In the sample size calculation, the 180-day CV death rate is assumed to be 9.0% in the placebo group, which is about 80% of 11.3% of all cause death observed in the placebo group in the RELAX-AHF study.

The interim analysis will be performed when 329 CV deaths are accrued. At the interim analysis, if Z-score of 2.786 (one-sided nominal $p = 0.0027$) is observed, which corresponds to HR of 0.735 (at least 26.5% RRR), the DMC may recommend to stop the study due to crossing the boundary. If there is no stopping at the formal efficacy interim analysis, the final analysis will need to have a Z-score of 2.072 (one-sided nominal $p = 0.0192$), which corresponds to HR of 0.838 (at least 16.2% RRR), to declare a significant study. ([contact], Cytel Inc., Cambridge MA, 2010).

If the observed overall event rate of the CV death endpoint during the course of the trial is much lower than expected based on the design assumptions (assessed on a blinded basis), adjustments may be made to the number of patients to be randomized in order to achieve the required number of events in the pre-planned timeframe (180 days) and thus to preserve the target study power.

For the sample size of 6,800, the unconditional power for the WHF endpoint and all three key secondary endpoints under various HRs (mean difference for Length of Stay) are summarized in the tables below:

Table 2-10 Assumed effect sizes for worsening heart failure and the key secondary efficacy variables on power calculation

	Assumed HR or mean difference
Worsening Heart Failure (placebo rate: 12.2%)	0.70
	0.80
All cause death (placebo rate: 11.3%)	0.80
	0.816
	0.83
Length of Stay (mean ±SD between placebo and serelaxin: 0.9 ±9.6 day)	0.9 day
	0.7 day
CV death or HF/RF rehospitalization (placebo rate: 34.1%)	0.85
	0.88

Note: Assumed placebo rates for all cause death and WHF and mean difference (mean + SD) in LOS between serelaxin and placebo were based on RELAX AHF study; placebo event rate of CV death or HF/RF rehospitalization was estimated to be 34.1% by assuming an exponential distribution with the same hazard as that observed through Day 60 in RELAX AHF study.

Table 2-11 Powers (unconditional) of primary and key secondary variables on selected scenarios

A) All cause death

Scenarios of effect sizes	All cause death Day 180*
All-cause death (HR=0.80); WHF (HR=0.70)	83
All-cause death (HR=0.816); WHF (HR=0.70)	77
All-cause death (HR=0.82); WHF (HR=0.70)	70
All-cause death (HR=0.80); WHF (HR=0.80)	82
All-cause death (HR=0.816); WHF (HR=0.80)	76
All-cause death (HR=0.82); WHF (HR=0.80)	70

Note: The true HR for CV death is assumed to be 0.78 in all scenarios.

*Power if one or both of the two primary variables are significant.

B) CVD, WHF, LOS and CVDR

Scenarios of effect sizes	CV death Day 180	WHF Day 5	LOS	CV death or HF/RF hosp.	Reject All
WHF (HR=0.7) – LOS (0.9 days) – CVD/rehosp (HR=0.85)	82	99	93	93	77
WHF (HR=0.7) – LOS (0.9 days) – CVD/rehosp (HR=0.88)	82	99	92	79	68
WHF (HR=0.7) – LOS (0.7 days) – CVD/rehosp (HR=0.85)	82	99	78	93	69
WHF (HR=0.7) – LOS (0.7 days) – CVD/rehosp (HR=0.88)	82	99	77	77	60
WHF (HR=0.8) – LOS (0.9 days) – CVD/rehosp (HR=0.85)	82	82	87	87	68
WHF (HR=0.8) – LOS (0.9 days) – CVD/rehosp (HR=0.88)	82	82	86	73	59
WHF (HR=0.8) – LOS (0.7 days) – CVD/rehosp (HR=0.85)	82	81	73	86	60
WHF (HR=0.8) – LOS (0.7 days) – CVD/rehosp (HR=0.88)	81	81	72	72	53

Note: The true HR for CV death is assumed to be 0.78 in all scenarios.

Note: The power for the WHF endpoint is approximated based on logrank test, but the analysis will be based on Gehan-Wilcoxon test.

3 References

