	
The key secondary efficacy endpoint of all-cause mortality through Day 180 will not be formally incorporated in a multiple testing procedure. It will be tested with a full <math>\alpha</math> (two-sided) by itself if one of the primary endpoints is statistically significant.
 
A sequentially rejective multiple testing procedure (Bretz, F et al 2009) is used in order to control the overall <math>\alpha</math> across the primary variables and the other two key secondary variables, length of hospital stay (LOS) and composite of CV death or rehospitalization due to HF/RF (CVDR).
 
Although there are two primary endpoints in this trial, the sample size is calculated based on CV death only. This is an event-driven trial with fixed maximum duration of 180 day follow-up period for each patient. The 180-day CV death rate is assumed to be 9.0% in the placebo group.
 
[REDACTED]
 
Using the proposed multiple testing procedure, the power for WHF is at least 80% with this sample size assuming at least 20% RRR and 12.2% placebo event rate for WHF.

Key words	Acute Heart Failure (AHF), Renal Impairment, Worsening Heart Failure,

## Amendment 5

Prevention of in-hospital WHF events is increasingly being recognized as a clinically relevant treatment goal of AHF. Following initial stabilization, in-hospital WHF occurs in 10-30% of hospitalized patients reflecting a severe manifestation of the AHF disease continuum requiring immediate intensification of rescue therapy (Torre-Amione et al 2009, Cotter et al 2010, Metra et al 2010a, Teerlink et al 2013) and represents a key unmet need for AHF patients. Thus after further consideration, the Executive Committee has recommended including the reduction of WHF events through day 5 as an additional primary endpoint. The following changes were made:

Sections 2.1 and 2.2 were updated to add reduction in worsening heart failure through Day 5 as a primary objective and delete it from the key secondary objectives.

Section 3.1 was updated to change the target number of CV deaths and the sample size needed to adjust for the alpha-split required to accommodate the additional primary objective.

Section 3.2 was updated to add WHF to the primary objective and include the WHF rationale.

Section 4 was changed to update the target number of CV deaths and the sample size needed to adjust for the alpha-split required to accommodate the additional primary objective.

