## 10.6 Interim analyses

It is planned to establish an external and Independent Data Monitoring Committee (DMC) to monitor patient safety data on a regular basis during the course of the study. For this study, it is likely DMC will review safety data in a regular frequency, e.g., every six months. DMC may request additional safety data review. Such safety analyses do not inflate the type I error for the primary efficacy hypothesis testing and thus require no multiplicity adjustments.

It is planned to have one formal interim efficacy analyses. The cut-off for this interim analysis is planned when the information fraction (number of confirmed CV deaths relative to the targeted total number of confirmed CV death at the study completion) of 60% is achieved. Some adjustment to the time of interim analysis may be made to coincide with the regular DMC meetings. One-sided tests will be performed and appropriate statistical adjustments for the interim analysis actually performed will be made to ensure the overall one-sided type I error of 0.02 (Lan-DeMets spending function to match an O'Brien-Fleming stopping boundary). For the interim analysis, the analysis dataset will comprise all patients who were randomized before the cut-off date.

The trial may only be concluded early for efficacy, if a significant difference between two treatment arms for the number of CV deaths is achieved by crossing the pre-specified boundary (irrespective of WHF results) at interim analysis and the overall risk/benefit profile is considered positive. Interim analysis will be performed by an external independent statistician at an external data analysis center, who will not be involved in the study conduct. The results will be reviewed by the independent DMC. Investigators and others who are involved in the conduct of the trial and in the analysis of the final trial results, or who have contact with study centers, will remain blinded to the treatment codes and interim analysis results until all monitoring decisions have been made and the database has been locked for final analysis.

Additional details of the interim analysis plan for efficacy and safety will be described in the DMC charter.

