Table 2-5 Primary, secondary and exploratory variables	15
Table 2-6 IV loop diuretics.....	23
Table 2-7 Safety risk and event of interest search specification	27
Table 2-8 Criteria for evaluating liver toxicity.....	31
Table 2-9 Nominal one-sided alpha at 70% randomized subjects accrued if CVD is rejected	34
Table 2-10 Assumed effect sizes for worsening heart failure and the key secondary efficacy variables on power calculation.....	36
Table 2-11 Powers (unconditional) of primary and key secondary variables on selected scenarios	36

Document History – Changes compared to previous version of RAP module 3.

Version	Date	Changes
Amendment 1	13-Aug-2015	
 -add the testing strategy for WHF and secondary endpoints in case of early stopping -add sensitivity analysis for WHF using logistic regression -add substudy population definition
Amendment 2	06-Feb-2017	
 - Clarify the method of mapping discharge visit to scheduled visits if scheduled visits are missing - Update the list of countries that recruited subjects (Table 2-3) - Remove subgroup category of lymphocytes and education level in Table 2-4 - Use FAS in section 2.1.9 – study medication summary. - Align presentation of non-IV concomitant medications with RELAX-AHF - Clarify definition of the censoring date for death endpoints (Adjudicated CV death, adjudicated all cause death) for patients who withdrew consent in countries where vital status data is publically available, in accordance with local laws and regulations - Clarify use of discharge date as the reference date for endpoint time to the composite endpoint of CV death or rehospitalization due to HF/RF during a follow-up period of 30 days post-discharge - Clarify the statistical method used for subgroup analysis of length of stay (LOS). Clarify the imputation rule for missing discharge information to align with RELAX-AHF - Clarify the imputation of signs and symptoms through Day 5 for subjects with WHF or died at hospital to align with RELAX-AHF - Addition of two new tables per ClinicalTrials.gov and EudraCT requirement -Update Safety risk and event of interest search specification (Table 2-7) - Clarify the ECG analysis population - Update the ECG categorical analysis, add analysis of newly occurring abnormalities in ECG morphology and remove ECG shift table to enable comprehensive assessment - Update liver function categorical analysis (Table 2-8)

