The Lan-DeMets spending function of the O'Brien-Fleming stopping boundary will then be applied to determine the nominal significance level at the interim analysis based on the one-sided alpha of 0.025.

The information fraction at the interim analysis for the three efficacy variables will be calculated as follows:

- WHF: number of randomized subjects at the interim analysis divided by 6800
It is expected that all randomized subjects will have complete WHF information through Day 5, as all patients will be followed up at least 14 days.
- LOS and CVDR: number of randomized subjects at the interim analysis divided by 6800 times 0.9

This assumes that 10% of the efficacy data will be missing at the interim analysis cutoff date.

Figure 2-2 **Sequentially rejective multiple testing procedure if DMC recommends stopping of the study due to overwhelming efficacy in CV death**

Applying the Lan-DeMets spending function of the O’Brien-Fleming stopping boundary if the DMC recommends stopping the study, assuming 70% of the randomized subjects are accrued at the interim analysis, the nominal one-sided alpha for the three efficacy variables are calculated as shown in the Table 2-9.

Table 2-9 **Nominal one-sided alpha at 70% randomized subjects accrued if CVD is rejected**

Efficacy variable	Updated alpha if CVD rejected	Information fraction	Nominal 1-sided alpha at interim analysis
WHF	$0.6 \times 0.025 = 0.015$	0.7	0.0036
LOS	$0.2 \times 0.025 = 0.005$	$0.7 \times 0.9 = 0.63$	0.0004
CVDR	$0.2 \times 0.025 = 0.005$	$0.7 \times 0.9 = 0.63$	0.0004

Note if the boundary is crossed for any of the remaining hypotheses, the multiple testing procedure will reject the hypothesis and update the graph. The nominal one-sided significance level will be re-calculated. The process continues until no hypothesis can be rejected.

For subjects not discharged by interim analysis cutoff date, the LOS will be imputed as the maximum of

- (1) mean value for subjects with actual LOS, including censoring at Day 60 and die in hospital
- (2) LOS at the cutoff date

All cause death will be tested at alpha of 0.025 (one-sided).

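### SAP Table 2-11 B's powers for WHF, LOS and CVDR leave out the early-stop tests of SAP 2.4; at 70% accrual WHF power at HR 0.80 is about 68–74% if every crossing stops the trial, not 81–82%

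*SAP*

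**What the plan says.** SAP 2.5 introduces its power tables with "For the sample size of 6,800, the unconditional power for the WHF endpoint and all three key secondary endpoints under various HRs". Table 2-11, which carries the title "Powers (unconditional) of primary and key secondary variables on selected scenarios", then lists eight scenarios in part B, all at a CV-death HR of 0.78. WHF power is 99% at HR 0.70 and 81–82% at HR 0.80; LOS and CVDR lie between 72% and 93%. The values are those of Protocol Table 10-2 B. The protocol synopsis makes a matching claim, tied to the planned graphical testing: "the power for WHF is at least 80% with this sample size assuming at least 20% RRR and 12.2% placebo event rate for WHF".

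The same SAP section sets the CV-death interim at 329 deaths with a boundary of Z = 2.786, at which "the DMC may recommend to stop the study due to crossing the boundary". Protocol 10.6 adds a second condition for early conclusion: the boundary must be crossed "at interim analysis and the overall risk/benefit profile is considered positive".

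SAP Amendment 1 records this change in the document history: "add the testing strategy for WHF and secondary endpoints in case of early stopping". The result is in SAP 2.4. After a stop for CV death, WHF, LOS and CVDR carry 0.6, 0.2 and 0.2 of one-sided 0.025 and are tested at the interim under a Lan-DeMets O'Brien-Fleming spending function. The SAP works one example, "assuming 70% of the randomized subjects are accrued at the interim analysis". For that example it says that "the nominal one-sided alpha for the three efficacy variables are calculated as shown in the Table 2-9": 0.0036 for WHF and 0.0004 each for LOS and CVDR, at information fractions 0.70, 0.63 and 0.63.

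**The concern.** The early-stop tests came in with SAP Amendment 1, but the SAP's power table still equals the protocol's, and the protocol contains no early-stop test for these three endpoints. If the table was not redone, it describes a trial that always reaches full information, whereas the SAP plans one that may test WHF, LOS and CVDR on part of the data at a fraction of the alpha. Nothing in the visible text of either document says that the stated powers exclude this path.

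WHF is a primary endpoint. A reader will take the table, and the synopsis figure of at least 80%, as properties of the plan as amended.

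**Working it through.** **Inputs.** From SAP 2.2.6.4, 2.4 and 2.5: one-sided alpha 0.02 for CV death and 0.005 for WHF; 329 CV deaths at 60% information, so about 329/0.6 = 548 in total; 6,800 patients, 1:1; WHF placebo rate 12.2%; LOS difference 0.9 or 0.7 day, SD 9.6; CVDR placebo rate 34.1%, HR 0.85 or 0.88.

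**Boundaries.** O'Brien-Fleming-type spending is α*(t) = 2[1 − Φ(z(α/2)/√t)].
- CV death, α = 0.02, t = 0.6: 2.326/√0.6 = 3.003, spend 0.0027, Z = 2.786. The final boundary by numerical integration is 2.072. Both match SAP 2.5.
- WHF, α = 0.015, t = 0.70: 2.432/√0.70 = 2.907, level 0.00365. LOS and CVDR, α = 0.005, t = 0.63: 2.807/√0.63 = 3.537, level 0.00041. Both match Table 2-9.

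**Drifts at full information.** For time-to-event endpoints |ln HR|·√events/2; for LOS δ/(SD·√(2/3400)).
- CV death: 0.2485 × √548/2 = 2.908.
- WHF, HR 0.80: serelaxin rate 1 − 0.878^0.80 = 9.885%; events 3,400 × (0.122 + 0.09885) = 751; drift 0.2231 × √751/2 = 3.057. At HR 0.70 it is 4.755.
- LOS: 3.865 (0.9 day) or 3.006 (0.7 day). CVDR: 3.789 (2,174 events) or 3.001 (2,204 events).

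**Chance of the early-stop path.** Interim CV-death drift: 0.2485 × √329/2 = 2.253. P(cross) = Φ(2.253 − 2.786) = Φ(−0.533) = 29.7%. Stopping is discretionary, so this is the upper limit of the stop probability.

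**WHF at HR 0.80, by hand, independent endpoints.** Once CV death is rejected, the graph gives WHF between 0.015 and 0.025.
- Full information: Φ(3.057 − 2.170) = 81.2% at 0.015; Φ(3.057 − 1.960) = 86.4% at 0.025.
- Stop at 70%: the drift is 3.057 × √0.70 = 2.558. At nominal 0.0036, power is 44.8%. With the whole 0.025, power is 54.8%.
- Cost at a fixed level: 0.297 × (81.2 − 44.8) = 10.8 points, or 0.297 × (86.4 − 54.8) = 9.4 points.
- Ceiling: give WHF the whole 0.025 on both paths, the most any graph allows. Power is 0.297 × 54.8 + 0.703 × 86.4 = 77.0%, still below 81–82%.

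**Full procedure, simulated** (120,000–200,000 trials per setting). Weights start at 0.8/0.2 and become 0.6/0.2/0.2 after CV death. The graph figures are not shown, so symmetric WHF edges and three versions of the LOS/CVDR edges were assumed, with correlations 0–0.5.

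Scenario WHF 0.80, LOS 0.9 day, CVDR 0.85, under independence, with the two graph versions that reproduce the table:

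| | CV death | WHF | LOS | CVDR |
|---|---|---|---|---|
| Table 2-11 B | 82 | 82 | 87 | 87 |
| Always full information | 81 | 82 | 88–89 | 88 |
| With SAP 2.4 tests at 70%, every crossing stops | 81–82 | 71 | 75–76 | 74 |

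The stated marginal powers therefore come back (within about 2 points) only when the early-stop path is left out.

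Results over all graph versions and correlations (WHF at HR 0.80; LOS/CVDR loss over the eight scenarios):

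| Randomized at interim | Crossings that stop | WHF % | WHF %, without the ill-fitting graph | LOS/CVDR loss, points |
|---|---|---|---|---|
| 65% | all | 66–72 | 67–72 | 7–19 |
| 70% | all | 68–74 | 70–74 | 5–17 |
| 70% | half | 73–77 | 75–77 | 2–9 |
| 80% | all | 72–78 | 74–78 | 2–12 |
| 90% | all | 76–80 | 78–80 | 1–7 |

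The ill-fitting graph lets LOS and CVDR pass alpha only to each other. It gives WHF only 78–79% even without stopping, but a similar loss (7–11 points). In the weakest scenario (WHF 0.80, LOS 0.7 day, CVDR 0.88), LOS and CVDR are 55–60% each against a stated 72%, at 70% accrual with every crossing stopped.

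**Is 70% plausible?** The pooled 180-day CV-death rate is (9.0% + [1 − 0.91^0.78])/2 = (9.0 + 7.09)/2 = 8.046%. So 329 deaths equal 329/0.08046 = 4,089 fully followed patients, 60% of 6,800. The documents do not give the recruitment length. Assuming uniform accrual and constant hazard, 10, 15, 24, 30, 36 or 48 months of recruitment puts 90, 80, 72.5, 70, 68 or 66% randomized at the interim.

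Mean-imputed LOS and dropout were not modelled.

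**The case against.** The strongest reply is that nothing is miscalculated: the table is right for 6,800 patients, which is what the lead-in says, and *unconditional* may mean only that power is not conditional on another endpoint being significant. That reading is possible. But neither phrase tells a reader that a planned path with up to a 29.7% chance is excluded, while Protocol 10.7 says the sample size, which rests on CV death, does account for the interim.

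The loss shown first is also an upper case. The 70% is the SAP's illustration, the DMC has discretion, and Protocol 9.4 requires Executive Committee ratification of major recommendations. This stands, and is why the results are given as ranges. Stopping on half of crossings still leaves WHF below 80%.

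Some settings behind the ends of the 68–74% range fit the stated table poorly. That also stands: the best-fitting settings give about 70–73%. The conclusion does not change.

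The protocol has no early-stop test for these endpoints, so its table does not contradict the protocol itself. The conflict arises with the amended SAP, and the synopsis sentence is affected because the procedure it relies on has been extended. Parts of the sample-size text are blacked out, so a caveat there cannot be ruled out.

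Finally, the path opens only after CV death has succeeded, and lower power afterwards is the price of alpha control. True, but that price is missing from the stated power.

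**Conclusion.** The concern holds. The powers in Table 2-11 B for WHF, LOS and CVDR are full-information powers and do not describe the plan with SAP 2.4 in it. For WHF at HR 0.80 the plan delivers less than stated unless accrual at the interim is near 90% or the DMC seldom stops. LOS and CVDR are affected in the same way.

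The size rests on the stop probability, the accrual fraction, assumed graph edges and assumed correlations, so no single replacement figure is defensible. WHF at HR 0.70 is barely affected (97–98% against 99%). CV-death power, the basis of the sample size, is unaffected. The point should be corrected, but it does not threaten the validity of any test.

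**What to change.** Do one of two things.

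1. Recompute SAP Table 2-11 B and Protocol Table 10-2 B with the SAP 2.4 stop path, over a stated range of accrual fractions, stop probabilities and correlations, and bring the synopsis claim for WHF into line. This costs a re-run of the power simulation and less favourable printed figures.
2. Label both tables and the synopsis sentence as full-information powers that do not allow for early stopping. This costs one sentence in each place.

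Do not write in a single new power as fact, because accrual at the interim and the DMC's decision are not fixed in advance. Neither option needs more patients or changes any test or alpha level.
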